If one or more study centers with Low-Level FCT (≤12.6 U/g) subjects have fewer than 10 subjects for the given analysis population, pooling of study centers will be required. Pooling of small study centers will be implemented as follows;

- Order the study centers, starting with those with the lowest numbers of Low-Level FCT (•12.6 U/g) subjects.
- The centers will then be combined in a consecutive upward order unless the total number of subjects exceeds the median number of subjects of all sites with 10 or more subjects.
- If this process does not capture all the study centers with fewer than 10 subjects, a second pooled study center will be created using the same process.
- This process will be continued until all study centers with fewer than 10 subjects are accounted for.

Again, this pooling algorithm will be repeated separately within each analysis population for which efficacy analyses will be run.

Unless otherwise indicated, p-values are two-sided and statistical significance is declared if the two-sided p-value is ≤ 0.05 . There is only one primary efficacy endpoint and one efficacy secondary endpoint. The primary endpoint will be tested at the two-sided 0.05 level of significance, and if significant, the secondary endpoint will be tested at the two-sided 0.05 level of significance. All other endpoints are considered exploratory and there will be no adjustment for multiple comparisons across these exploratory endpoints.

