8.6.1 Primary Efficacy Analysis

The primary efficacy endpoint is the change from Baseline (score at Screening Part 1) to Week 12 visit in the ABC Irritability/Agitation (ABC-I) in the Low Level FCT ITT population as defined in Section 3. Descriptive statistics of ABC-I and change from Baseline ABC-I will be presented at Week 12 for each treatment group. Mean change in Baseline ABC-I at Week 12 will be compared across treatment groups using a mixed model repeated measures (MMRM) model with terms for treatment, study center, visit, and the treatment by visit interaction. The model will also include Baseline ABC-I score as a covariate and subject will be a random effect. An unstructured covariance matrix will be used for the within-subject correlation. Kenward-Rogers' approximation will be used to estimate degrees of freedom. The SLICE option will be employed to examine differences across treatments at specific time points, with the focus being on the Week 12 change from Baseline. Two-sided 95% confidence intervals of the difference between treatment means of the primary endpoint will be constructed using MMRM model estimates for the mean. Tests of hypotheses will be two-sided and will be based on the contrasts between CM-AT and placebo within the MMRM model.

An assessment of treatment-by-study center interaction on the change from Baseline (score at Screening Part 1) to Week 12 ABC-I will be carried out using analysis of variance (ANOVA). Included in the ANOVA model will be main effects for treatment, investigative center and Baseline ABC-I and the treatment-by-center interaction effect. A 0.10 level of significance will be used to assess the interaction. A non-significant interaction or an interaction significant but only quantitative in nature will support the pooling of results across study centers for the final analysis. For the PP, ITT, and All Randomized analysis sets, a treatment-by-low-level status interaction will be assessed in a similar manner as the treatment-by-study center interaction.

If statistical significance, in favor of CM-AT, is shown on the primary efficacy endpoint (FCT \leq 12.6 U/g) in the Low-Level ITT analysis set, the study will be considered a success statistically.

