For completeness, though not of primary interest, descriptive statistics of ABC-I and of the change from ABC-I will be presented at each visit, and treatment group comparison p-values on mean change from Baseline ABC-I to each visit will be calculated from the MMRM model discussed above.

Missing ABC-I Data: The primary analyses will be based on the MMRM model with available data discussed above. As a sensitivity analysis, the above analyses will be repeated where, first, multiple imputation using the monotone linear regression approach will be used to impute missing primary endpoint data at each visit via SAS PROC MI; included as covariates in the linear model will be age, sex, race, ABC Irritability measured at previous visits (including the randomization visit), Baseline FCT, and investigative center.

Ten complete datasets will be created (the linear regression approach to multiple imputation assumes monotone missing data pattern; if such a pattern does not exist, then prior to each of the 10 linear regression imputations, non-monotone missing ABC-I data will be imputed via the MCMC approach on ABC-I across visits to create a monotone missing data pattern). Once complete datasets are generated, the primary MMRM model will be applied to each of these datasets with the results will be combined into a single estimate of the treatment difference on the change from Baseline to each visit using SAS PROC MIANALYZE. The focus is on the treatment difference on the change from Baseline to the Week 12 ABC-I as the primary analysis.

As an additional tertiary sensitivity analysis, the Last-Observation Carried Forward (LOCF) method will be applied prior to carrying out the MMRM analysis. For subjects who prematurely withdrew, the last efficacy measurement obtained prior to premature withdrawal (even if the last measurement is the Baseline measurement or the measurement obtained at the randomization visit) will be carried forward to each visit following the withdrawal prior to carrying out the MMRM.

8.6.2 The secondary efficacy endpoint of ABC-L will be analyzed and compared between treatments in a similar manner as the primary endpoint. Again, the Low-Level FCT ITT analysis set is primary, but all ITT, All Randomized and PP analysis sets will be analyzed.

8.6.3 Exploratory Endpoints:

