For continuous exploratory endpoints, treatments will be compared on change from Baseline in a similar manner as the primary endpoint at Week 12 and each Post-Baseline visit except for multiple imputation and assessment of treatment-by-study center interaction effects. For CGI-S, an endpoint for which there is no Baseline value, treatments will be compared in a similar manner as the primary endpoint on the CGI-S value itself (as opposed to a change from Baseline) without a Baseline value of the endpoint as a covariate. There will be no adjustment for multiple comparisons.

For dichotomous exploratory endpoints (stool test, weight gain/loss), no formal statistical hypothesis testing will be performed to compare the treatment groups on these results.

The number and percentage of subjects experiencing the dichotomous endpoint will be presented for each treatment group. For completeness, this analysis will be repeated for each visit.

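### The multiple-imputation models leave out randomised treatment, so the MI sensitivity estimate at Week 12 is generally biased if CM-AT has an effect at any visit

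*SAP*

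**What the plan says.** SAP 8.6.1 makes the observed-data model primary: "The primary analyses will be based on the MMRM model with available data discussed above". MI is a sensitivity analysis, and LOCF is a further one labelled tertiary. The protocol synopsis promises analyses with and without imputation.

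The MI has three stages.

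- Non-monotone gaps come first: "non-monotone missing ABC-I data will be imputed via the MCMC approach on ABC-I across visits".
- The remaining missing scores are filled by monotone linear regression: "included as covariates in the linear model will be age, sex, race, ABC Irritability measured at previous visits (including the randomization visit), Baseline FCT", with investigative center closing the list.
- Then "the primary MMRM model will be applied to each of these datasets". That model is a "mixed model repeated measures (MMRM) model with terms for treatment, study center, visit, and the treatment by visit interaction", with Baseline ABC-I as covariate.

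Section 8.6.2 extends this to ABC-L: "The secondary efficacy endpoint of ABC-L will be analyzed and compared between treatments in a similar manner as the primary endpoint". Section 8.6.3 exempts continuous exploratory endpoints, which are analysed "in a similar manner as the primary endpoint at Week 12 and each Post-Baseline visit except for multiple imputation". Section 8.6 applies the efficacy analyses to every ITT, All Randomized and PP set.

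**The concern.** An imputation model should contain the variable whose effect the analysis will estimate. Here it does not. A subject who leaves after Week 4 gets a Week 12 score predicted from covariates and earlier scores, by a regression pooled over both arms. That prediction carries only as much of the treatment difference as the earlier scores pass on. The part of the Week 12 effect that they do not carry is lost for every imputed subject. This happens even under missing at random, so it is a specification fault and not a finding about the missing data.

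At stake is how the sensitivity analysis reads. Under missing at random, a well-specified MI should largely agree with the MMRM. As written, the two can differ because of the omitted term alone, and the gap could be taken as fragility. If an early benefit has disappeared by Week 12, MI would lend slight false support. The affected results are the MI analyses of ABC-I and ABC-L in the ITT and All Randomized sets. PP sets require a Week 12 ABC-I score, so no ABC-I value is imputed there at Week 12.

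**Working it through.** **1. The plan's own figures (SAP 8.1).** Changes are -3.7 (SD 7.0) and -0.6 (SD 5.0), a difference of 3.1. Pooled SD = sqrt((49 + 25)/2) = 6.08. With 82 per group, SE = sqrt(49/82 + 25/82) = 0.95, and noncentral-t power is 0.900. Then 82/0.85 = 96.5, so 97; and 97/0.60 = 161.7, so 162. All reproduce. This point does not touch them.

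**2. Share missing at Week 12.** The plan anticipates 15% withdrawal. Timing is not given. Spread evenly over six visit intervals, it is 2.5% per interval. Reading the ITT rule as requiring a post-randomization score removes the first 2.5%, leaving 12.5/97.5 = 12.8% missing. In the All Randomized sets it is 15%.

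**3. Formula.** Let d be the vector of treatment effects by visit (zero at screening and randomization), and let m be the fraction whose last score is at a given visit. With 1:1 allocation, the pooled covariance seen by the imputation regression is the within-arm covariance plus 0.25 dd'. Let w be the resulting weights on the observed scores. The large-sample estimate is

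d(12) - sum of m × g, where g = d(12) - (sum of w × earlier effects).

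The bias is zero if every g is zero, which is assured only when there is no effect at any visit.

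**4. An example that can be done by hand.** Assume compound symmetry 0.5 and variance 37 (so the SD of change is 6.08), with all 15% leaving after Week 2. Partialling out the two pre-treatment scores removes 2 × 18.5²/55.5 = 12.33 from each variance and covariance.

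- Constant 3.1: w = (18.5 + 2.40 - 12.33)/(37 + 2.40 - 12.33) = 8.57/27.07 = 0.317. The effect carried is 0.317 × 3.1 = 0.98. Estimate = 3.1 - 0.15 × 2.12 = 2.78.
- Linear growth (Week 2 effect 3.1/6 = 0.517): w = 6.567/24.733 = 0.266, carried 0.14. Estimate = 3.1 - 0.15 × 2.96 = 2.66.
- Week 12 only: nothing is carried. Estimate = 0.85 × 3.1 = 2.635.
- Faded (3.1 at Week 2, zero at Week 12): w = 6.17/27.07 = 0.228, carried 0.71. Estimate = 0.15 × 0.71 = 0.11 where the truth is 0.

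**5. The same check when variance grows over visits.** Assume a random intercept (SD 5), a random slope (SD 6 over the 14 weeks from screening to Week 12) and residual SD 2, with variances scaled by 37/44 to keep the SD of change at 6.08. The SD rises from 4.9 to 7.4. For a constant 3.1, the weights on screening, randomization and Week 2 are -0.43, 0.38 and 1.11. The Week 2 weight exceeds one, so the effect carried is 1.11 × 3.1 = 3.44 and the estimate is 3.1 + 0.15 × 0.34 = 3.15. The sign has reversed.

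**6. Ranges over assumed structures.** Low-Level FCT ITT, even withdrawal unless stated. The first column covers compound symmetry 0.5 and 0.7 and AR(1) 0.8 and 0.9.

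| Effect over visits | Compound symmetry, AR(1) | Random intercept and slope |
|---|---|---|
| Constant 3.1 | 2.92-3.02 | 3.04-3.22 (2.88-3.24 over all timings) |
| Linear growth to 3.1 | 2.78-2.87 | 2.67-3.04 over all timings |
| 3.1 at Week 12 only | 2.70 | 2.70 |
| Faded to zero | 0.12-0.22 (0.09-0.31 over all timings, AR(1) to 0.95) | up to about 0.4 |
| None at any visit | 0.00 | 0.00 |

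Under compound symmetry and AR(1) (up to 0.95), the first three shapes span 2.63-3.08 over all timings. In the All Randomized sets with even withdrawal they span 2.63-2.95. An effect waning from 3.1 to 1.5 gives 1.47-1.53, so the bias can nearly cancel.

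**7. Does adding treatment cure it?** In simulations with withdrawal depending on the previous score, including treatment recovered 3.1 as 3.07-3.14 and a faded effect as -0.02 to +0.02.

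**8. The MCMC step.** With one intermittent visit missing and a constant 3.1, the imputed arm difference is 2.2-2.3 under compound symmetry. Under AR(1) it is 1.8 at Week 2 and 3.0-3.1 at Weeks 4-10. This reaches Week 12 only indirectly.

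**The case against.** The strongest reply is that nothing decisive depends on MI. That stands. The available-data MMRM is primary, and the success rule in 8.6.1 looks only at the primary endpoint. The gate in 8.2 is fixed without MI: "The primary endpoint will be tested at the two-sided 0.05 level of significance, and if significant, the secondary endpoint will be tested". The interim statistic also comes from the MMRM. A reader might infer that the trial's conclusion or its Type I error is compromised. The documents do not support that, and with no effect at any visit the MI estimate is unbiased too.

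A reader might also infer that the omission always pulls the estimate toward zero, so that MI is merely conservative. That does not hold either. Step 5 shows a constant effect exaggerated, and the SAP's unstructured covariance does not exclude such a pattern. A faded effect gives a spurious benefit.

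It can be said that treatment is implied, or that the bias is small. On the first, the SAP writes out the covariates, and such a list is what gets programmed; if treatment is meant, stating it costs nothing. On the second, the shift is indeed modest, but it is avoidable, and it falls in the analysis meant to show whether the result survives another treatment of missing data.

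**Conclusion.** The omission is plain in the text, and it makes the MI estimate at Week 12 generally biased when CM-AT has an effect at any visit. In the structures examined, linearly growing and Week-12-only effects are attenuated. A constant effect is attenuated under compound symmetry or AR(1), but can be unbiased or slightly exaggerated when variance grows over visits. A faded effect leaves a small spurious benefit.

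For a true 3.1 the estimates lie at about 2.6 to 3.2. The largest shift, about 0.47, is 0.47/0.95 = 0.49 of the planning standard error. For a faded effect the spurious 0.1 to 0.4 points is at most 0.4/0.95 = 0.42 of it. These sizes rest on assumed correlation, trajectory and withdrawal timing, none of which the documents give, so they are illustrations and not limits. Confidence is high for the omission and the remedy, and lower for direction and size. The SAP should be corrected, although no decision rule depends on it.

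**What to change.** In SAP 8.6.1, add randomised treatment as a covariate in the imputation regression at every visit, and as a fully observed 0/1 variable in the MCMC step. State that the same applies to ABC-L under 8.6.2. Because the monotone regression is fitted visit by visit, a main-effect term already lets the effect differ between visits.

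This is preferable to imputing separately by arm. Center is an imputation covariate, and 194 low-level subjects over about 35 sites is about 5.5 per site, or 2.8 per site per arm, before pooling.

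The cost is one term in the text and in the PROC MI calls, and one parameter per regression. No design element changes. The corrected MI will largely agree with the MMRM and will not test departures from missing at random, so it should not be presented as doing so.

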8.1 Sample Size

Sample size is based on:

- The primary efficacy variable -
 - Change from Baseline (score at Screening Part 1) to Week 12 for the Aberrant Behavior Checklist (ABC) subscale for Irritability
- The primary analysis set of Low-level FCT ITT subjects.
- 1:1 randomization scheme

Previously reported Sponsor data indicating that 60% of autistic children have pathologically low levels of FCT formed the basis for the following calculations. Assuming a -3.7 ± 7.0 ABC Irritability change from Baseline to Week 12 of for CM-AT and -0.6 ± 5.0 for Placebo, a sample size of 82 evaluable low-level subjects per treatment group (active and placebo) yields 90% power to declare a statistically significant difference between treatments at a two-sided 0.05 level of significance. To account for an anticipated 15% early withdrawal, 97 low-level subjects will be randomized per treatment group (active and placebo). A total of 162 subjects per group will be randomized to achieve 97 randomized low-level subjects per group (active and placebo).

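### SAP 8.6.1 plans no sensitivity analysis that tests loss of benefit after withdrawal; add control-based imputation with a tipping point, and put treatment in the imputation model

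*SAP*

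**What the plan says.** SAP 8.6.1 makes the MMRM on available data primary, in the Low-level FCT ITT set. Two missing-data checks follow. In the first, "multiple imputation using the monotone linear regression approach will be used to impute missing primary endpoint data". Its listed covariates are age, sex, race, earlier ABC-I scores, Baseline FCT and center. Randomized treatment is not listed, and the SAP does not say that the imputation is run by arm. In the second, labelled tertiary, "the Last-Observation Carried Forward (LOCF) method will be applied prior to carrying out the MMRM analysis". The value carried may be the Baseline or randomization-visit score if nothing later exists.

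The protocol synopsis says only that analyses will be done with and without imputation. Neither document names a reference-based, delta-adjusted or tipping-point analysis. SAP section 8.6 repeats the analyses in the All Randomized and PP sets. Section 3 earmarks the Low-level FCT All Randomized set for a sensitivity analysis and labels the PP (completer) sets exploratory.

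Withdrawal is expected. SAP 8.1 states: "To account for an anticipated 15% early withdrawal, 97 low-level subjects will be randomized per treatment group". Success is declared on the primary analysis alone (SAP 8.6.1).

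**The concern.** A sensitivity analysis for missing data should relax the assumption behind the primary result in a direction that could overturn it. In a 12-week trial of a treatment for symptoms, the obvious direction is that a child who stops CM-AT loses the benefit.

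The planned checks do not ask that question. The imputation stays within missing at random. LOCF leaves that framework, but it holds a child who improved and then withdrew at the improved score through Week 12. It also adds carried scores to the sample as if they had been measured, which makes the standard error smaller. The MMRM, the imputation and LOCF could therefore all agree without showing whether the finding survives loss of benefit in the roughly one child in seven expected to leave. What is at stake is how robust a positive result can be said to be.

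**Working it through.** **Inputs, all from SAP 8.1.** Effect and SDs: "Assuming a -3.7 ± 7.0 ABC Irritability change from Baseline to Week 12 of for CM-AT and -0.6 ± 5.0 for Placebo". Allocation: "1:1 randomization scheme". Also 82 evaluable and 97 randomized low-level children per arm, 15% withdrawal, 90% power and two-sided 0.05. The difference is 3.7 − 0.6 = 3.1. The root-mean-square SD is √((7² + 5²)/2) = √37 = 6.083.

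**1. The plan's own figures.** n = 2 × (1.96 + 1.2816)² × 37 / 3.1² = 80.9, so 81 by the normal approximation. The t-based calculation gives 82 (power 0.9004). Then 82/0.85 = 96.5, so 97, and 97/0.60 = 161.7, so 162. The plan's figures are reproduced.

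**2. Primary analysis.** Evaluable children: 97 × 0.85 = 82.45 per arm. SE = 6.083 × √(2/82.45) = 0.947. Power = Φ(3.1/0.947 − 1.96) = 0.905.

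**3. LOCF.** Let f be the share of the Week 12 effect present at the last visit of those who withdraw. Assume equal withdrawal in both arms, unrelated to outcome, and the same SD at every visit. The expected difference is 3.1 × (0.85 + 0.15f). All 97 count as observed, so SE = 6.083 × √(2/97) = 0.873.

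| f | Difference | Power |
|---|---|---|
| 0 | 2.63 | 0.855 |
| 0.25 | 2.75 | 0.883 |
| 0.5 | 2.87 | 0.907 |
| 0.75 | 2.98 | 0.927 |
| 1 | 3.10 | 0.944 |

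Power equals that of the primary analysis when 0.85 + 0.15f = √0.85, so f = (0.922 − 0.85)/0.15 = 0.48. For 10% to 25% withdrawal the break-even is 0.49 to 0.46.

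**4. Withdrawn CM-AT children revert to the placebo mean.** The expected difference is 3.1 × 0.85 = 2.635. With the evaluable-subject SE, the pass probability is Φ(2.635/0.947 − 1.96) = 0.79. At 10%, 20% and 25% withdrawal it is 0.86, 0.72 and 0.64.

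**5. Simulation.** This used 97 per arm, six visits, monotone withdrawal unrelated to outcome, ten imputations with Rubin's rules and 1,500 to 2,000 runs (Monte Carlo error about 0.7 to 1 point). The effect profiles, withdrawal timing and correlation (0.8 per visit step) are assumptions. A missing-at-random imputation with treatment in the model stands in for the MMRM.

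| Case | Missing at random | LOCF | Reference-based |
|---|---|---|---|
| Linear effect, uniform withdrawal | 0.91 | 0.90 | 0.83 |
| Early plateau, uniform withdrawal | 0.92 | 0.94 | 0.87 |
| Late effect, early withdrawal | 0.88 | 0.83 | 0.81 |
| Linear effect, 20% CM-AT / 10% placebo | 0.91 | 0.88 | 0.79 |

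Another run of the plateau case gave 0.835 for the reference-based analysis, so the 0.87 should be read loosely. A check of the linear case with constant correlation 0.5 gave the same pattern.

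**6. The imputation as listed, without treatment.** In the same simulations the mean difference fell to 2.77 (power 0.86) in the linear case and 2.64 (power 0.81) in the late-effect case. Withdrawn children in both arms are predicted from a model fitted to the pooled arms.

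**The case against.** Five points can be made against this.

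- **LOCF can be strict.** A reader might infer that LOCF is simply as easy to pass as the primary analysis. The documents do not support that. They give no withdrawal timing, effect time course or visit-level variability. Below f of about 0.48 LOCF is harder, and with a late effect and early withdrawal it is about 5 points harder and close to the reference-based result. It also freezes placebo improvers. This stands, so only a range can be given.
- **LOCF in the All Randomized sets.** There it can carry a Baseline or randomization-visit score and so give no credit for treatment. That is true. But the primary set requires a post-Baseline ABC-I, so on the ordinary reading of that term the clause has little effect there.
- **The imputation already attenuates.** It does, and it is not a mere repeat of the primary analysis. But its shrinkage comes from leaving treatment out of the covariate list, and it affects both arms. It cannot be read as a test of a stated assumption.
- **No decision depends on it.** No sensitivity analysis has a pass rule, and LOCF is only tertiary. This stands and limits the importance of the point.
- **The 0.79 is approximate.** It applies an evaluable-subject SE to an estimate that uses all subjects. This stands, which is why the simulated 0.81 to 0.87 is given beside it.

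**Conclusion.** The gap is real and is an optional improvement. No planned analysis tests a stated departure from missing at random toward lost benefit after withdrawal. At the plan's 15% withdrawal, LOCF power runs from 0.855 to 0.944 against 0.905 for the primary analysis, so whether LOCF is a harder test cannot be known in advance. Reversion to the placebo mean would lower the expected difference from 3.1 to about 2.6, with pass probability about 0.79 in closed form or 0.81 to 0.87 in simulation with equal withdrawal. In all four simulated cases the reference-based analysis was the strictest of the three compared.

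These figures take the plan's effect and SDs as true and withdrawal as unrelated to outcome. Two stronger inferences should be resisted. The lower pass probability is not evidence that the trial is underpowered or needs resizing, because it describes a stress test. Nor is the success decision affected, since it rests on the primary analysis. The gain is in the credibility of a positive result.

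**What to change.** Amend SAP 8.6.1 before unblinding:

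- In the Low-level FCT ITT set, specify control-based imputation, with withdrawn CM-AT children imputed from the placebo profile, as the sensitivity analysis outside missing at random.
- Add a delta-adjusted tipping point on the CM-AT arm. State the grid of deltas in advance and report the value at which significance is lost.
- Put these in place of LOCF, or ahead of it with LOCF kept as tertiary. Either meets the need.
- Include randomized treatment in the missing-at-random imputation model, or run that model by arm, and say which. Apply the same choice to the MCMC step used when missingness is not monotone.

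The cost is a little programming within the PROC MI and PROC MIANALYZE steps already planned. The downside is a sensitivity estimate likely to be less favourable than LOCF. The primary analysis, success rule and sample size do not change.
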